Three (3) subjects will be treated with a single administration of 2×10^7 (20 million) UCMSCs delivered via peripheral intravenous infusion.

Group 2 (3 subjects)

Three (3) subjects will be treated with a single IV administration of 2×10^7 (20 million) BMMSCs delivered via peripheral intravenous infusion.

The subjects in the high dose (Groups 3 & 4) will not be treated until the subjects in the low dose (Groups 1 & 2) have completed their one-month follow-up assessments and safety measures have been reviewed to confirm that there have been no treatment emergent SAE's.

Group 3 (3 subjects)

Three (3) subjects will be treated with a single IV administration of 1×10^8 (100 million) UCMSCs delivered via peripheral intravenous infusion.

Group 4 (3 subjects)

Three (3) subjects will be treated with a single IV administration of 1×10^8 (100 million) BMMSCs delivered via peripheral intravenous infusion.

Randomized Phase (30 subjects)

Group A (10 subjects – UCMSCs)

Ten (10) subjects will be treated with a single administration of 1×10^8 (100 million) UCMSCs delivered via peripheral intravenous infusion.

Group B (10 subjects – BMMSCs)

Ten (10) subjects will be treated with a single administration of 1×10^8 (100 million) BMMSC delivered via peripheral intravenous infusion.

Group C (10 subjects – Placebo)

Ten (10) subjects will be treated with a single administration of placebo delivered via peripheral intravenous infusion.

Subjects in each pilot phase group (Group 1, 2, 3 and 4) will not be treated less than 5 days apart.

The randomized portion of the study will be conducted after a full review of the safety data from the Pilot Phase by the DSMB

Patients will be randomized in a 1:1:1:1 ratio to one of the 3 groups in the randomized phase. For subjects randomized to B (BMMSCs); the cells will be derived from a healthy allogeneic bone marrow donor (obtained by iliac crest aspiration).

For subjects randomized to Group A (UCMSCs); the cells will be derived from a healthy allogeneic umbilical cord tissue donor.

Route of Administration	Peripheral Intravenous Infusion
Duration of Study Participation	12 months (Follow-up will be at 2 weeks, 1 Month, 3, 6, and 12 months.)
Inclusion Criteria	
1. Provide written informed consent2. Subjects age ≥ 21 and ≤ 95 years at the time of signing the Informed Consent Form.3. Each subject must have endothelial dysfunction. Endothelial dysfunction Criteria:

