3. STUDY DESIGN

3.1 Description of the Study

A Pilot Phase will be performed to test the safety of dose and volume of cells administered via peripheral intravenous infusion. The first three (3) subjects in-group 1 (UCMSCs) will be treated first and safety will be fully assessed. Only if there is no evidence of treatment emergent SAEs in Group 1, treatment of subjects in Group 3 be undertaken.

The subjects in the high dose (Groups 3 & 4) will not be treated until the subjects in the low dose (Groups 1 & 2) have completed their one-month follow-up assessments and safety measures have been reviewed to confirm that there have been no treatment emergent SAE's. Treatment emergent SAE's, defined as the composite of: death, non-fatal pulmonary embolism, stroke, hospitalization for worsening dyspnea and clinically significant laboratory test abnormalities, prior to proceeding with the treatment of further subjects.

Subjects in each pilot phase group (Group 1, 2, 3 and 4) will not be treated less than 5 days apart.

Subjects in the pilot phase will receive a telephone call 5 days post infusion (+/- 1 day) to review adverse events.

The randomized portion of the study will be conducted after a full review of the safety data from the Pilot Phase by the DSMB.

Following the pilot study (12 subjects), thirty (30) subjects that meet inclusion criteria will be scheduled to undergo peripheral intravenous infusion.

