7.2.4 Week 2 Visit

See Table 11 for the procedures and assessment to be performed for the week 2 visit of the study. Outpatient visits should be completed as close to the scheduled visit dates as possible. There will be a window of +/- 2 days for the week 2 study visits.

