8.1.5 Subject Stopping Guidelines

This guideline is to be used to indicate boundaries requiring discussion by the Data and Safety Monitoring Board (DSMB) and is designed to assist the independent DSMB in overseeing the study. The DSMB may also request additional interim analyses and develop other criteria including provision for monitoring of potential late effects to determine when to intervene in the enrollment or treatment of subjects in the study. The first more conservative stopping guideline is to monitor subjects for unexpected SAEs where there is a reasonable possibility that the study product or administration procedure caused the event within 30 days of administration including subject death, grade 3 myocardial infarction, grade 3 hemodynamically unstable ventricular tachycardia or grade 3 LV perforation. Study accrual and further treatment of subjects will be put on hold if any subjects experience one of these events. The DSMB will be notified within 24 hours of the occurrence of these events and will be convened within 3 business days to review the event and study.

The following are subject stopping guidelines:

5. Any subject who develops persistent (that is, still existing more than 3 hours after the end of IP infusion) cardiorespiratory signs or symptoms (for example, shortness of breath, tachypnea, tachycardia, Bradycardia, hypotension, or palpitations) will continue with all scheduled follow-up if such follow-up is considered safe in the opinion of the Investigator.
6. Any subject whose infusion is stopped due to cardiorespiratory distress will receive no further IP infusions but will continue with all scheduled follow-up if such follow-up is considered safe in the opinion of the Investigator.
7. Any subject who develops any sign or symptom that, at the discretion of the Investigator, warrants the discontinuation of infusion will receive no further IP infusions but will continue with all scheduled follow-up if such follow-up is considered safe in the opinion of the Investigator.
8. Infusion of the IP may be stopped if there is an adverse event that the Investigator believes is related to the IP or if there is an issue with the IP infusion.

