8.12 Timeframes for Submitting SAE Reports

Once an Investigator becomes aware that an SAE has occurred in a study subject, he/she will record the information in the electronic data record within 48 hours. Any fatal or life-threatening event must be reported within 24 hours. If the Investigator does not have all information regarding an SAE, he/she will not wait to receive additional information before recording the event in the data system and completing as much information known at the time of the submission. The reporting timeframes for any SAE occurring during the study are summarized in Table 12.

TABLE 12
Serious Adverse Event Reporting Requirements

	Initial Reports		Follow-Up Reports
Type of SAE	Fatal or Life-Threatening	Other SAEs	Any SAE
Reporting Timeframes	24 hours	48 hours	48 hours
Documents Required	24 hours: Complete as much information in the electronic data system that is known. 48 hours: Fully complete all AE forms	Fully completed AE forms	Updated AE Forms

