
Procedures post-infusion:

1. Vital signs will be monitored at 15 minutes, 30 minutes, 1 hour, and 2 hours post IP infusion
2. The subject will be monitored for a minimum of 2 hours post IP infusion with continuous pulse oximetry
3. If the O₂ saturation decreases to < 90% over a continual period of 3 – 5 minutes, then supplemental oxygen may be added or increased during the two hours post-infusion observation period.
4. If at the end of the 2-hour observation period, if a subject's O₂ saturation stays below 90% then the subject will be provided additional oxygen to maintain a saturation of >90% at room air up to 4 hours post infusion.
5. After the minimum two-hour observation period, the subject will be continuously monitored and discharged the following day, if no complaints are experienced, such as shortness of breath or other objective signs of cardiorespiratory compromise.
6. Subjects not meeting criteria for discharge will be assessed by the Investigator during the observation period to further determine hospitalization otherwise not specified in the protocol.

Subject Stopping Guidelines:

1. Any subject who develops persistent (that is, still existing more than 3 hours after the end of IP infusion) cardiorespiratory signs or symptoms including hypoxemia (defined per oxygenation criteria of 93% on room air at rest, or shortness of breath, tachypnea, tachycardia, hypotension, or palpitations) will continue with all scheduled follow-up if such follow-up is considered safe in the opinion of the Investigator. The infusion will be stopped if the oxygen saturation does not return to >93% within 3 minutes of initiating supplemental oxygen or if the subject requires greater than 2L/min supplemental oxygen to achieve the required saturation of >93%. If a subject requires the addition of oxygen, it will be continued for 4 hours after the completion of the infusion. At that time, oxygen will be weaned off to maintain a saturation >93% on room air.

2. Any subject whose infusion is stopped due to cardiorespiratory distress will receive no further IP infusions but will continue with all scheduled follow-up if such follow-up is considered safe in the opinion of the Investigator.

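### In the pilot phase, the next subject in a group can be infused before the previous subject's Day 5 safety call, because dosing is not made to wait for that call.

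*Combined protocol and SAP*

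**What the plan says.** Two rules stand close together in Section 3.1. The first sets the stagger: subjects within each pilot group "will not be treated less than 5 days apart". The Protocol Synopsis repeats it. The second sets the safety call: "Subjects in the pilot phase will receive a telephone call 5 days post infusion (+/- 1 day) to review adverse events". The call is repeated in the note under Table 11. No sentence connects the two.

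The other contacts and controls around a pilot infusion are these:

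- **Inpatient observation.** Under Appendix 1, after the two-hour observation period "the subject will be continuously monitored and discharged the following day, if no complaints are experienced".
- **First clinic visit.** This is Week 2 (Day 14). Section 7.2.4 states: "There will be a window of +/- 2 days for the week 2 study visits".
- **Between dose levels.** Section 3.1 says the high-dose groups "will not be treated until the subjects in the low dose (Groups 1 & 2) have completed their one-month follow-up assessments" and the safety data have been reviewed.
- **Between phases.** Sections 9.3 and 9.4.3.3 place the DSMB review after all pilot subjects have been followed for 30 days.
- **Event-driven hold.** Section 8.1.5 names a short list of serious, possibly product-related events within 30 days and says: "Study accrual and further treatment of subjects will be put on hold if any subjects experience one of these events".
- **SAE reporting.** The reporting times in Section 8.12 start "Once an Investigator becomes aware that an SAE has occurred in a study subject".

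**The concern.** The pilot phase exists to check safety before more people are exposed, and the stagger only helps if something is learned during it. The interval and the call are both set at 5 days, which suggests the call could inform the next dose. As written, a team that follows the protocol exactly can still make the call after that dose.

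The exposure is narrow. Anything that appears during the infusion or overnight is known by Day 1. What can be missed is an event that begins at home and that the subject does not mention until asked. The primary safety endpoint in Section 2.2.1 covers a full month and gives stroke, pulmonary embolism and admission for worsening dyspnea as examples. These can begin after discharge, and an admission elsewhere might not reach the investigator for some days. The call is the scheduled means of finding out.

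**Working it through.** The plan gives no figure to reproduce here; the check is a count of days.

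**Inputs**

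- Minimum interval within a group: 5 days, with exactly 5 allowed (Section 3.1, synopsis).
- Call window: 5 − 1 = Day 4 to 5 + 1 = Day 6 (Section 3.1, Table 11).
- Planned discharge: Day 1 (Appendix 1).
- Week 2 visit window: 14 − 2 = Day 12 to 14 + 2 = Day 16 (Section 7.2.4).
- Pilot size: 4 groups × 3 subjects = 12 (Section 3.1, synopsis).

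**Step 1: order of the call and the next infusion.** Compare each permitted call day with the day of the next infusion in the group.

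| Gap to next infusion | Call on Day 4 | Call on Day 5 | Call on Day 6 |
|---|---|---|---|
| 5 days | before | same day, order not set | one day after |
| 6 days | before | before | same day, order not set |
| 7 days | before | before | before |

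Only a gap of 7 days or more places every in-window call before the next infusion.

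**Step 2: one group at minimum spacing.** Infusions fall on Days 0, 5 and 10, counted from the first subject.

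- Infusion 2 (Day 5): the first subject's call can be as late as Day 6, so 6 − 5 = 1 day late. Nobody in the group has yet had a scheduled contact after discharge. The time since the first subject's discharge is 5 − 1 = 4 days.
- Infusion 3 (Day 10): the second subject's call window is 5 + 4 = Day 9 to 5 + 6 = Day 11, so the call can be 11 − 10 = 1 day late. The first subject's call was due by Day 6, so only the second subject's is outstanding.
- The first subject's Week 2 visit is on Day 12 at the earliest, after infusion 3.

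**Step 3: all four groups, worst case.** Second subjects: 4 × 1 = 4. Third subjects: 4 × 1 = 4. Total: 8 of 12 infusions precede the immediately previous subject's call. In 4 of these 8 there has been no scheduled post-discharge contact with anyone in the group.

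**Step 4: with the remedy.** If the call must precede dosing, or the gap is at least 7 days and calls are made in window, the count is 0 of 12.

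**Step 5: do other rules set the order?** The one-month review acts between low and high dose. The wording in Section 3.1 about proceeding to further subjects belongs to that same step. The full assessment of Group 1 is tied to starting Group 3. The DSMB review acts between phases. The hold in Section 8.1.5 and the reporting times in Section 8.12 apply once an event is known. None of them requires contact with the previous subject before the next one in the group is infused.

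**The case against.** The best case against making the change runs as follows.

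- **It takes a coincidence.** Five days is a floor and not a schedule, and Day 6 is one of three permitted call days. One centre controls both events and can call on Day 4 or infuse later without any amendment. The figure of 8 of 12 assumes the least favourable timing in every group. This stands: the figure is an upper bound, and nothing in the documents says how likely it is.
- **There are strong holds.** A single listed event under Section 8.1.5 stops further treatment, with the DSMB told within 24 hours and convened within 3 business days. The same section also stops treatment if more than one subject has cardiorespiratory signs that persist or end the infusion. These rules narrow the gap considerably. They do not close it, because they need someone to know of the event.
- **The call would change few decisions.** Most events in the pilot composite in Section 3.1 are major and would usually come to light, and a telephone call cannot detect a laboratory abnormality. This also stands, and it is why the point ranks as minor. It leaves an admission elsewhere, or symptoms the subject did not think to report.
- **The remedy does not bring a clinic visit forward.** This is true. All three subjects can still be infused before the first Week 2 visit and its laboratory tests. The remedy secures the call and no more.

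A staggered design with an event-driven hold is defensible. The change proposed is a refinement, not the correction of an error.

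**Conclusion.** The concern holds as a minor design point. Conduct that complies fully with the protocol can place the only early post-discharge safety contact after the next exposure in the same group. The size is at most 8 of 12 pilot infusions, each by one day. That bound assumes minimum spacing and a Day 6 call every time, with calls made in window and discharge on Day 1 as planned. A missed or late call would lengthen the lag. The risk is confined to events that start after discharge and are not volunteered; acute infusion reactions are already covered.

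**What to change.** Add to Section 3.1 and to the synopsis: *The next subject in a pilot group will not be infused until the previous subject's Day 5 call has been completed and reviewed by the investigator.* For consistency, the note under Table 11 could refer to the same rule. By default, an unreachable subject means a wait; if the sponsor prefers another fallback, it should be written down.

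Tying dosing to the completed call is better than lengthening the stagger to 7 days, because the longer interval works only when the call is made in window.

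The cost is one sentence in two places, an occasional delay of about a day when the call is made in window, and a longer delay if a subject cannot be reached. Sample size and analysis are unaffected.

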3.2. RANDOMIZATION STUDY

This Phase I/II, randomized, blinded, placebo-controlled study is designed to evaluate the safety and tolerability of UCMSCs versus BMMSCs in subjects with chronic inflammation due to the metabolic syndrome and to explore potential efficacy at baseline, 3 and 6 months.

In the randomized phase of the trial, product will be prepared by ISCI GMP laboratory personnel. The selected personnel will not have contact with the investigators or subjects for this trial. At the time of administration, opaque tubing will be used to maintain double blinding. Treatments will be administered once and will consist of 1×10^8 (100 million) UCMSCs, 1×10^8 (100 million) BMMSCs or placebo. After each infusion, subjects will be monitored for immediate complications.

Continued safety and tolerability with review of adverse events (AEs) will be monitored at each visit. Efficacy parameters (6MWT and QOL questionnaires) will be assessed at various study visits. Clinical laboratory tests to assess safety will be performed at every clinic visit, excluding the baseline visit.

4. SUBJECT SELECTION

4.1 Inclusion Criteria

In order to participate in this study, a subject MUST:

1. Provide written informed consent
2. Subjects age ≥ 21 and ≤ 95 years at the time of signing the Informed Consent Form.
3. Each subject must have endothelial dysfunction. Endothelial dysfunction criteria: impaired flow-mediated vasodilation (FMD $< 7\%$).
4. At the time of enrollment, each subject must meet at least 3 out of the 5 criteria under the harmonized definition of the metabolic syndrome, consisting of the following:

Table 10. Criteria for the Metabolic Syndrome

Measure	Categorical Cut-Off Points	Alternative Indicators
Waist circumference	US defined: ≥ 102 cm (males) or ≥ 88 cm (females)	Ethnic and country-specific definitions
Elevated triglycerides	≥ 150 mg/dL (1.7 mM)	Drug treatment for elevated triglycerides
Reduced HDL	Males: <40 mg/dL (1.0 mM)	Drug treatment for reduced

	Females: <50 mg/dL (1.3 mM)	HDL-C
Elevated blood pressure	Systolic \geq 130 mm Hg and/or Diastolic \geq 85 mm Hg	Antihypertensive drug treatment for a history of hypertension
Elevated fasting glucose	\geq 100 mg/dL	Drug treatment of elevated glucose

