PBMC	Peripheral Blood Mononuclear Cells
PSURs	Periodic Safety Update Reports
QOL	Quality of Life Questionnaires
RNA	Ribonucleic Acid
RPMS	Relapsing Remitting Multiple Sclerosis
RPR	Rapid Plasma Reagin
SAE	Serious Adverse Events
SAO ₂	Oxygen Saturation
SAP	Statistical Analysis Plan
SCF	Stem Cell Factor Antigen
SF-36	Short Form – 36

SLE	Systemic Lupus Erythematosus
SLEDAI	Systemic Lupus Erythematosus Disease Activity Index
SQOL-F	Sexual Quality of Life - Female
SW	Stroke Work
TE-SAE	Treatment Emergent Serious Adverse Events
TNF α	Tumor Necrosis Factor-alpha
TTC	Triphenyltetrazolium chloride
UC	Umbilical Cord Tissue
UCMSCs	Umbilical Cord Tissue derived Mesenchymal Stem Cells
VEGFR2	Vascular endothelial growth factor receptor-2
VO ₂	Oxygen Consumption
VDRL	Venereal Disease Research Laboratory test
WBC	White Blood Count
WJ	Wharton's Jelly

Protocol Synopsis

Sponsor: Interdisciplinary Stem Cell Institute (ISCI) at the University of Miami Miller School of Medicine

Name of Study Therapy: Allogeneic Umbilical Cord Tissue derived MSCs (UCMSCs) versus Bone Marrow derived Mesenchymal Stem Cells (BMMSCs)

Title of Study: A Phase I/II, Randomized, Blinded, Placebo-controlled Comparative study to evaluate the Safety and Potential Efficacy of Intravenous Infusion of Umbilical Cord Tissue (UC) derived Mesenchymal Stem Cells (MSCs) Versus Bone Marrow (BM) derived MSCs to evaluate cytokine suppression in patients with chronic inflammation due to Metabolic Syndrome. The CERES Trial.

Study Center: ISCI at the University of Miami Miller School of Medicine	Phase of Development: Phase I/II
--	---

Objectives:

Primary: To compare the safety of UCMSCs and BMMSCs administered intravenously in patients with chronic inflammation due to Metabolic Syndrome.

Secondary:

- To demonstrate the efficacy of UCMSCs and BMMSCs administered intravenously in patients with chronic inflammation due to Metabolic Syndrome as assessed by (see Table 9 in Section 2.2.2):
- symptom related quality of life
- cardiovascular status
- inflammatory cytokines
- endothelial function
- lipid profile
- glucose homeostasis
- 1year survival

Design and Investigational Plan: This Study is intended as a safety assessment prior to a full comparator study. In this Study, cells administered via intravenous infusion (IV) will be tested in 42 patients in two phases (Pilot and Randomized):

Pilot Phase (12 subjects)

Group 1 (3 subjects)

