Patients with the metabolic syndrome have double the risk of developing CVD in 5 – 10 years versus normal individuals, and a 5-fold increased risk of developing T2DM^{1,3,5}. Furthermore, compared to individuals without the syndrome, patients with the metabolic syndrome are 2 to 4- times more likely to have a stroke, 3 to 4-times more likely to have a myocardial infarction (MI), and 2-times more likely to die from any such an event^{5,6}. The incidence of the metabolic syndrome has reached epidemic proportions worldwide, with >40% of US adults ≥20 years of age classified as having the metabolic syndrome^{3,7}. Thus, effective treatment of the metabolic syndrome is a paramount health concern.

Inflammation caused by the Metabolic Syndrome

Dysregulated inflammation is a considerable key physiological correlate of the metabolic syndrome, in which affected persons commonly manifest a proinflammatory and prothrombotic

state⁸. Inflammatory markers are predictors of cardiovascular events and progression to diabetes in healthy individuals, including individuals with metabolic syndrome. For example, those with metabolic syndrome are more likely to have elevated C-reactive protein (CRP), fibrinogen, interleukin-6 (IL-6), red blood cell distribution width (RDW) and D-dimer⁸.

Excess adiposity promotes the metabolic syndrome in at least 2 major ways^{8,9}. First, the adipose cells release adipose tissue-derived non-esterified fatty acids (NEFAs) that inhibit insulin signaling¹⁰. Second, the increased adipose cells (especially abdominal) releases adipokines, which are cytokines that promote a pro-inflammatory state¹¹. These promote diminished whole-body sensitivity to insulin. Consequently, the pancreas initially increases insulin secretion to maintain normoglycemia. The result is a somewhat asymptomatic phase which can last many years, but which nevertheless leads to the development of a pro-inflammatory and pro-thrombotic state accompanied by dyslipidemia and hypertension, and eventually the co-morbidities that include T2DM and CVD.

Endothelial Dysfunction, Endothelial Progenitor Cells, and the Metabolic Syndrome

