The hypothesis of this trial is that suppressing cytokines levels in subjects with metabolic syndrome will cause a decrease in the chronic inflammation and endothelial dysfunction caused by the disease^{34,35,36,37,38}.

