1.2 Rationale

We have analyzed TNF α levels for our subjects for the CRATUS Study, allogeneic BMMSCs were tested in a range of 20M MSCs to 200M MSCs in a Phase 1/2 clinical study in 45 Aging Frailty subjects (BB-IND#15679). The study contained a run in pilot phase testing single intravenous administration of 20M, 100M or 200M MSCs, followed by a randomized, placebo-controlled double blind Phase 2 single intravenous administration of 100M MSC or 200M MSCs or placebo in 30 subjects. Results showed no significant changes in any of the treatment arms. However, the average baseline TNF α levels for the subjects in all 3 arms were less than half those in the Phase 1 study, and were already close to the low level for the reference range (1.2 – 15.3 pg/mL). No significant changes in other biomarkers were observed.

As we know that frailty is hypothesized to result from a complex interplay of biochemical and multi-systemic changes that may result in decreased physiologic reserves in older adults and biological mechanism that underlies the decline in physical function associated with aging frailty is chronic inflammation³⁵. This response is initially characterized by a local release of cytokines, responsible for the amplification and regulation of the inflammatory cascade.

[figure not shown]
Cytokines are also involved in numerous physiological functions, such as muscle and bone tissues turnover, immunoregulation, and hematopoiesis and their circulating levels have been related to several disease processes, primarily atherosclerosis and cardiovascular disease. Chronically elevated inflammatory biomarkers have been observed in the presence of acute and chronic conditions, including atherosclerosis, Parkinson's disease, type 2 diabetes mellitus, sarcopenia, functional disability, cerebrovascular disease, coronary heart disease, CHF and arthritis. Inflammation exerts detrimental effects on muscle, bone, cardiac function, hematopoiesis and cognition^{34,39,40}.

Not surprisingly, data from our frailty studies indicate an association between the frailty syndrome and elevated levels of pro-inflammatory mediators including IL-6, C-reactive protein (CRP), and TNF α ^{41,41,42,42,43,43}. Although these various inflammatory markers are correlated with each other, the relative importance of these markers as predictors of frailty or physical decline has not been established.

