2.2.2. Secondary Endpoints (Efficacy)

(Assess at Baseline, Week 2, Month 1, Month 3, and Month 6 following IV allogeneic MSC infusion). Assess EPC-colony forming units (CFUs) 2. Assess circulating inflammatory markers (IL-1, IL-6, TNF α , and CRP) 3. Assess circulating angiogenic factors known to mobilize and recruit EPCs (VEGF, SDF-1 α , and SCF)4. Assess FMD%.

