7. STUDY PROCEDURES

7.1. Time and Events Schedule

The Time and Events Schedule for the conduct of this study is shown in **Table 11**

Schedule of Assessments
Table 11: Time and Events Table

VISIT	Screening + 45 days	Baseline (0 to -4 weeks prior to Day 0)	Day 0	Week 2 (Day 14) ± 2 days	Month 1 (Day 30) ±1 weeks	Month 3 (Day 90) ±4 weeks	Month 6 (Day 180) ±6 weeks	Month 12 (Day 365) ±2 weeks
Informed Consent	X							
Full Medical History	X							
Physical Exam	X	X	X	X	X	X	X	X
Vital Signs ¹	X	X	X	X	X	X	X	X
12-lead (ECG)	X	X	X	X	X	X	X	X
Concomitant Medications	X	X	X	X	X	X	X	X
Randomization		X						
Infusion Treatment (IP)			X					
6 Minute Walk Test			X			X	X	
4 Meter Gait Speed Test			X			X	X	
QOL Questionnaires (EQ-5D, SF-36, IIEF (Male), SQOL-F(Female))		X			X	X	X	
Laboratory Testing ²								
Review Adverse Events		X	X	X	X	X	X	X
Brachial Ultrasound ³	X	X				X		
Dobutamine Stress Echo (DSE) ⁴	X						X	

Subjects in the pilot phase will receive a telephone call 5 days post infusion (+/- 1 day) to review adverse events

- 1- Weight, Height (will only be collected at screening)
- 2- See table 12 for specific tests done at each time point
- 3- Brachial ultrasound to assess endothelial function should be completed in the morning prior to 12p.m. Instruction for completing this assessment are outline in Appendix 3 of this protocol
- 4- Dobutamine Stress Echocardiogram (DSE) will be performed, at screening and at the Month 6 follow-up visit. Instructions for completing the (DSE) are outlined in Appendix 2 of this protocol. If the stress test needs to be stopped due to unforeseeable side effects and cannot be completed on a subject, this will not prevent them from being able to take part in the study.

Schedule of Laboratory Testing
Table 12: Time and Events Table

VISIT		SCR	BSL	DAY 0	W2	M 1	M 3	M 6	M 12
Standard Labs	CBC with Differential ¹	X		X	X	X	X	X	
	Comprehensive Metabolic Panel ²	X		X	X	X	X	X	
	PT, INR, PTT	X							
	Uric Acid, Pro BNP, hsCRP, IL6, Fib, D-dimer, TNFa,	X		X	X	X	X	X	
	Lipid Profile ³	X		X	X	X	X	X	
	Urinalysis	X		X		X	X	X	
	HbA1c	X				X	X	X	
	Pregnancy (childbearing women) ⁴	X		X					
Biomarkers / Immune	SST / PRA ⁵			X				X	
	MNCs ⁶			X	X	X	X	X	
EPCs	Endothelial Blood Samples ⁷		X				X		
Gene Expression	DNA ⁸			X					
	RNA			X				X	
Viral Serology	Infectious Disease Tests ⁹	X							

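### The plan describes its subjects as having chronic inflammation, but no entry criterion requires it and no cytokine analysis uses the baseline level, so a null cytokine result would be hard to interpret

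*Combined protocol and SAP*

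**What the plan says.** The title in the Protocol Synopsis states the aim as "to evaluate cytokine suppression in patients with chronic inflammation due to Metabolic Syndrome". The primary and secondary objectives (2.1.1, 2.1.2) and section 3.2 use the same description of the subjects. Section 1.1 ends: "The hypothesis of this trial is that suppressing cytokines levels in subjects with metabolic syndrome will cause a decrease in the chronic inflammation", together with the endothelial dysfunction.

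Besides consent and age, section 4.1 has two requirements. The first is "Each subject must have endothelial dysfunction", defined as FMD below 7%. The second is that "each subject must meet at least 3 out of the 5 criteria under the harmonized definition of the metabolic syndrome": waist, triglycerides, HDL, blood pressure and fasting glucose. For four of these five, Table 10 lists drug treatment as an alternative indicator. None of the 18 exclusions in section 4.2 sets a level for an inflammatory marker.

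Section 2.2.2 makes the cytokines a secondary endpoint ("Assess circulating inflammatory markers": IL-1, IL-6, TNF-alpha and CRP). One row of Table 12 ("Uric Acid, Pro BNP, hsCRP, IL6, Fib, D-dimer, TNFa") is drawn at Screening, Day 0, Week 2 and Months 1, 3 and 6. No section uses those values to select, stratify or adjust. Section 9.2 provides descriptive statistics and two-sided tests at 0.05, calls efficacy exploratory, and mentions no baseline covariate.

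**The concern.** The population named in the objectives is not the population the criteria select. Section 1.1 links metabolic syndrome to inflammation only as a tendency: "those with metabolic syndrome are more likely to have elevated C-reactive protein (CRP", among other markers. Some enrolled subjects may therefore have low levels.

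The protocol shows that it knows baseline level can matter. The opening paragraph of section 1.2 reports no significant change in any arm of the randomised phase of the sponsor's earlier frailty trial. It then adds that baseline TNF-alpha was below half the Phase 1 level "and were already close to the low level for the reference range". Here, FMD is given room to improve by an entry cut-off, while the cytokines in the title get neither a cut-off nor a baseline-adjusted analysis.

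Two things are at stake. A null cytokine result could mean that the cells do nothing or that there was little to suppress, and the planned outputs could not tell these apart. A positive result would be reported for inflamed patients who were never selected as such. The synopsis presents this study as a step before a full comparator study, so either misreading could carry forward.

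**Working it through.** **1. Label against criteria.** The title, objectives and section 3.2 say chronic inflammation. Sections 4.1 and 4.2 contain no inflammatory marker. The mismatch follows from setting these side by side.

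**2. The protocol's own baseline figure.** Inputs are the mean baseline TNF-alpha values in section 1.2 (pg/mL):

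| | 20M | 100M | 200M | Placebo |
|---|---|---|---|---|
| Phase 1 | 4.14 | 5.30 | 5.88 | – |
| Phase 2 | – | 3.14 | 3.33 | 2.35 |

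The opening paragraph puts all three Phase 2 arms below half of Phase 1.

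- Same dose: 3.14 / 5.30 = 59%; 3.33 / 5.88 = 57%.
- Against the Phase 1 mean, (4.14 + 5.30 + 5.88) / 3 = 5.11: 61% (100M), 65% (200M), 46% (placebo).
- Against each Phase 1 group separately: the cell arms run from 3.14 / 5.88 = 53% to 3.33 / 4.14 = 80%; placebo from 2.35 / 5.88 = 40% to 2.35 / 4.14 = 57%.

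The statement does not reproduce for either cell arm. It holds for placebo on some comparisons only.

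**3. Two accounts of one result.** The opening paragraph gives no significant change in any arm and a low baseline. The later text around Figures 1 and 2 says TNF-alpha was elevated at baseline and fell significantly in both phases, with a significant within-group fall at 100M in the randomised phase and some fall in every arm, placebo included. Both accounts cannot stand.

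**4. How far low baseline explains anything.** The reference range given is 1.2 to 15.3 pg/mL, a width of 14.1. Position in the range is (mean − 1.2) / 14.1.

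- Phase 1: 21%, 29%, 33%.
- Phase 2: 14%, 15%, 8%.

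All six means are inside the range and in its lower third. The Phase 1 groups nevertheless fell significantly, by over 50% according to the Figure 1 legend. At 100M the distance to the lower limit was 5.30 − 1.2 = 4.10 in Phase 1 and 3.14 − 1.2 = 1.94 in Phase 2, a ratio of 47%. That fits less room for a fall. It does not show that a fall is impossible, because 1.2 is a reference limit and the documents do not call it a floor.

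**5. Why adjust for baseline.** In the earlier randomised phase the placebo arm started at 2.35 / 3.14 = 75% and 2.35 / 3.33 = 71% of the two cell arms. Differences of that size are plausible again with 10 per arm, and they distort an unadjusted comparison of change. With 30 subjects in three arms, residual degrees of freedom at one visit go from 30 − 3 = 27 to 30 − 4 = 26 with one covariate.

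**The case against.** The best defence has three parts. First, the primary endpoint is safety, efficacy is declared exploratory, section 9.1 claims no power, and FMD, EPC colonies and angiogenic factors have no shown dependence on cytokine level. All of that stands, and it confines the point to the cytokine endpoint and the population label.

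Second, metabolic syndrome plus FMD below 7% is a reasoned proxy, since section 1.1 describes both as pro-inflammatory states. That makes the entry rule defensible as a choice. It does not make chronic inflammation an established feature of each subject.

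Third, the later account in section 1.2 undercuts the low-baseline explanation. This is correct, and it is why the two accounts need reconciling before either is relied on.

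A reader might infer more: that subjects with normal markers cannot show suppression, and that power collapses as a result. Assume a 50% fall in responders, none in the others, log-scale SD 0.5 and 10 per arm. Power is then about 83%, 53%, 26% and 10% when 100%, 75%, 50% and 25% of subjects can respond. The arithmetic is sound, but the documents do not support the premise. The Phase 1 means were within the reference range and fell. Neither the SD nor the responder share is given anywhere. The 50% is an uncontrolled within-arm change, whereas placebo also fell in Phase 2.

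**Conclusion.** The concern holds in a limited form. The stated population is broader in name than the entry criteria justify, and the planned analysis would leave a null cytokine result ambiguous. The ambiguity rests on one modest assumption, that lower baseline levels leave less room for a fall; the documents are consistent with this but do not prove it. How much any effect would be diluted cannot be derived from them. The safety endpoint is untouched.

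Separately, and without any assumption, section 1.2 contradicts itself on the earlier randomised phase, and its below-half statement fails for both cell arms.

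A reader might also conclude that an inflammatory entry threshold is required. The documents do not support that either. It would be an enrichment choice with a recruitment cost. Section 1.2 reports minimal effect on IL-6 and CRP and says the relative importance of the markers is not established, so no marker or value follows from the plan.

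**What to change.** 1. **Population.** In the objectives, and later in the conclusions, name the subjects as having metabolic syndrome with endothelial dysfunction (FMD below 7%), unless the sponsor chooses to add an inflammatory entry criterion.
2. **Section 1.2.** Reconcile the two accounts of the earlier randomised phase, covering whether baseline was low or elevated, whether TNF-alpha changed, and the below-half statement.
3. **Section 9.2.** Analyse each cytokine on the log scale by ANCOVA, with treatment arm and the marker's own log Day 0 value as covariate. State that the Day 0 sample precedes infusion. IL-1 is an endpoint but is not named in the Table 12 row, so confirm that it has a Day 0 value.
4. **Reporting.** Tabulate the baseline distribution of each marker by arm, which the generic baseline summaries in section 9.1 do not name. Plot response against baseline level as description only. A formal test is not worthwhile: under the illustrative assumptions above and an even split into 5 per arm per stratum, power is about 31% for the interaction and 49% within the raised stratum.

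The cost is wording, a little more analysis, and one degree of freedom per model. No new test or visit is needed for the markers already in Table 12.
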